### **STUDY PROTOCOL**

The plant cell wall derived RG-I (from chicory or carrot) and maltodextrin (placebo) in capsuled form will be provided by the food company NutriLeads B.V (Wageningen, The Netherlands), which has run tests of safety of the products and warrants their food grade quality and safety. The administration of RG-I will be done via a human intervention study of parallel arms, randomized, placebo – controlled, double blinded design (proof of concept study).

#### **Task 1: Evaluation of the prebiotic and intestinal inflammatory effects of RG-I daily supplementation**

The dietary fibre from different RG-I sources will be tested for its prebiotic and immunomodulatory potential. Thus, the effects of these fibres on short chain fatty acid (SCFA) profile, microbiota composition, microbiota-associated metabolites and intestinal inflammatory markers will be investigated.

In this Task, quantification of the aforementioned parameters will be performed in fecal samples which will be obtained from the study participants every week during their participation in the study. Furthermore, for this purpose subjects will complete questionnaires related to their diet; Food Frequency Questionnaire (an extract of the online tool that will be used for this purpose and a Gastrointestinal Symptom rating scale (GSRS) in the beginning and in the end of the interventional period.

**Task 2: Evaluation of the immunomodulatory, gut-brain interaction and lifestyle related effects of RG-I daily supplementation**

The dietary fibre from different RG-I sources will be tested for their immunomodulatory and lifestyle related effects. The effects of fibres on immune activation markers related peptides markers will be investigated from blood samples collected from the study participants. Furthermore, to assess the effects of RG-I supplementation in lifestyle, subjects will complete questionnaires related to their physical activity (IPAQ) and quality of life (EQ-5D-5L) at the beginning and at the end of the interventional period for this Task.

**STATISTICAL ANALYSIS**

The groups will be of equal size and a time dependent analysis will be performed using a logistic generalized estimating equations (GEE) model via a stepwise approach. age, gender and BMI will be included AS confounding parameters. As fixed factors group (treatment versus placebo: dummy variable), time, time squared and the interaction between group and time will be taken into account. When the outcome does not warrant a GEE approach a Chi square analysis with expectation will be performed. Calculations will be done for a two-sided statistical evaluation at a significance level of 0.05.

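### The only named methods, a logistic GEE and a chi-square test, do not fit the quantified weekly fecal outcomes, and no cut-point or continuous-outcome model is given

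*Combined protocol and SAP*

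**What the plan says.** The STATISTICAL ANALYSIS section is one short paragraph. It states that "a time dependent analysis will be performed using a logistic generalized estimating equations (GEE) model via a stepwise approach". Age, gender and BMI are adjusted for, and on the other model terms it says: "As fixed factors group (treatment versus placebo: dummy variable), time, time squared and the interaction between group and time will be taken into account". If an outcome does not suit GEE, a chi-square test replaces it. Testing is two-sided at 0.05. No outcome is named in this section.

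The outcomes appear in the two task sections:

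- **Task 1, what is measured:** "the effects of these fibres on short chain fatty acid (SCFA) profile, microbiota composition, microbiota-associated metabolites and intestinal inflammatory markers will be investigated".
- **Task 1, how:** "quantification of the aforementioned parameters will be performed in fecal samples". Sampling is weekly.
- **Task 1, symptom questionnaire:** "Gastrointestinal Symptom rating scale (GSRS) in the beginning and in the end of the interventional period".
- **Task 2, blood:** "immune activation markers related peptides markers will be investigated from blood samples collected from the study participants". Neither the scale nor the sampling times are stated.
- **Task 2, physical activity (IPAQ) and quality of life (EQ-5D-5L):** completed "at the beginning and at the end of the interventional period for this Task".

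**The concern.** A logistic model needs a binary outcome, or at least a proportion, and a chi-square test needs categories. A metabolite or inflammatory-marker concentration is neither. Applied as written, the plan requires each concentration to be categorised, and it does not say where.

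Three things are at stake. Splitting a concentration discards information and so costs power. A threshold not fixed in advance can be chosen after seeing the data, which inflates the type I error. And the result is an odds ratio at an arbitrary threshold, whereas a proof-of-concept study needs the size of the change in the marker.

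The plan also leaves open which model term is the tested effect and what would make an outcome unsuitable for GEE.

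**Working it through.** **Step 1: match outcomes to methods.**

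| Outcome | Nature in the text | Served by logistic GEE or chi-square as written? |
|---|---|---|
| Metabolites, intestinal inflammatory markers | Quantified, weekly | No, unless cut at an unstated threshold |
| SCFA profile, microbiota composition | Quantified, weekly; may be expressed as shares | Only if a logit link on proportions is intended, which is not stated |
| GSRS, IPAQ, EQ-5D-5L | Questionnaires, start and end | No cut or responder rule given |
| Task 2 blood markers | Scale and timing not stated | Cannot be judged; nothing here rests on them |

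The protocol text and the statistical section contain no linear model, identity link, transformation, responder rule or threshold.

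**Step 2: what categorising would cost.** The plan states no power figure to reproduce. Its only usable input is two-sided alpha 0.05. Everything else is assumed: outcome normal (or normal after transformation), small shift, 80% power on the continuous scale. If a fraction *eff* of the information is kept, power = Φ(2.8016·√eff − 1.96).

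*One measurement, cut at proportion p:* eff = φ(z_p)² / [p(1−p)].

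- p = 0.50: eff = 0.637; power = Φ(2.8016·√0.637 − 1.96) = 61%.
- p = 0.25: eff = 0.539; power = 54%.

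*Repeated samples, median split:* a latent correlation r becomes (2/π)·arcsin(r). Then eff = (2/π) × (generalised least squares information with the binary correlation matrix) / (the same with the latent matrix). The design per arm is intercept plus time for the group-by-time term, and intercept only for the averaged difference. For an exchangeable structure the group-by-time case reduces to (2/π)(1−r) / [1 − (2/π)arcsin r]. At r = 0.3 this is 0.637 × 0.700/0.806 = 0.553.

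| Tested term | Structure | r = 0.3 | r = 0.5 | r = 0.7 |
|---|---|---|---|---|
| Group-by-time | Exchangeable, any number of samples | 0.553 (55%) | 0.477 (49%) | 0.377 (40%) |
| Group-by-time | AR(1), 5 samples | 0.667 (63%) | 0.654 (62%) | 0.598 (58%) |

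Entries are information kept, with power in brackets. With 4 to 8 samples the AR(1) group-by-time values run from 0.550 to 0.708. For the difference averaged over 4 to 8 samples, the exchangeable structure keeps 0.765 to 0.859 (power 69% to 74%) and AR(1) keeps 0.722 to 0.811 (66% to 71%).

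*Simulation check:* AR(1), 5 samples, 150 per arm (assumed), the plan's fixed factors without covariates, robust standard errors, 1,500 runs per setting. Identity-link GEE power was 0.81, 0.81 and 0.79 for r = 0.3, 0.5 and 0.7. Median-split logistic GEE power was 0.64, 0.63 and 0.58, in line with the AR(1) row above.

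**Step 3: a threshold picked from the data.** Take cuts at 25%, 50% and 75%, one measurement, a large sample, and corr(Z_a, Z_b) = a(1−b)/√[a(1−a)b(1−b)] for a < b. This gives 0.577 for neighbouring cuts and 0.333 for the outer pair. By simulation, P(max |Z| > 1.96) is about 0.12.

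**Step 4: whether an identity link alone is enough.** For a lognormal marker with a multiplicative effect, an untransformed analysis keeps s²/(exp(s²) − 1), where s is the log-SD. This is 0.880, 0.745 and 0.582 at s = 0.5, 0.75 and 1.0. It falls to the median split's 0.637 at s = 0.92. The choice of scale therefore matters as much as the link.

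**Step 5: two-occasion outcomes (minor).** With only a start and an end measurement, the five columns (intercept, group, time, time squared, group-by-time) have rank 4. Time squared is redundant with time, but the group-by-time estimate does not change.

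**The case against.** The strongest defence is that the word logistic is loose drafting. The paragraph is brief, the study calls itself proof of concept, nothing states an intention to dichotomise, and the fallback clause shows that the authors expected the method to vary by outcome. On that reading the loss of power may never occur. Part of this stands: what is shown is a mismatch between stated methods and stated outcomes, and the power loss follows only if the text is applied literally. But the fallback does not help, because it too needs categories. GEE can handle continuous data through another link, but the plan names the logistic form.

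A logit link can also be fitted to proportions without any cut. That is a fair point for SCFA or taxon shares, though the plan does not say it is meant, and it does not help with concentrations.

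The illustrated loss runs from 14% to 62% of the information, depending on the term, correlation structure and number of samples, so no single figure can be quoted for this trial. That stands too. So does the limit that the opening pages were not in the text read; the statistical section itself is present and shows no redaction.

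Finally, replacing the link does not settle the stepwise approach, the single treatment dummy when the protocol names chicory and carrot as RG-I sources, or the behaviour of robust standard errors if groups are small. These are separate questions and do not remove the mismatch.

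**Conclusion.** The concern holds, and the plan should be corrected before analysis. The named methods do not fit the concentrations that Task 1 sets out to measure, so the analyst must either depart from the plan or invent thresholds. This conclusion rests on the text alone.

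The size is illustrative. If outcomes are dichotomised, the scenarios computed turn 80% power into 40% to 74%, and a threshold picked from three quartile cuts gives about 12% type I error. These figures assume normality on some scale, a small shift and within-person correlations of 0.3 to 0.7, none of which the documents supply. Outcomes that are binary by nature are not affected.

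**What to change.** For quantified outcomes, replace the logistic GEE with an identity-link GEE or a linear mixed model. Keep the listed group, time, time squared and group-by-time terms and the adjustment for age, gender and BMI. Then:

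- Fix the analysis scale for each outcome in advance: log for skewed concentrations, with a rule for values below detection, and a log-ratio or other compositional method for microbiota composition. This is essential, as step 4 of the working shows.
- Name the term that is the treatment effect, and report mean differences or ratios with 95% confidence intervals.
- If a logit link on proportions is intended for any outcome, say so.
- Keep logistic GEE and chi-square for outcomes that are binary or categorical by nature or have a pre-specified threshold, and define when chi-square replaces GEE.
- Minor: for GSRS, IPAQ and EQ-5D-5L, drop time squared or use baseline-adjusted ANCOVA.

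The same revision is the natural place to say what the stepwise approach covers, so that selection cannot remove the tested term.

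The cost is SAP wording and a little analysis work, with the same data, participants and software.

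### The planned GEE states no provision for missing samples, so outcome-related drop-out that differs by arm could bias the group-by-time effect

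*Combined protocol and SAP*

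**What the plan says.** The Statistical Analysis section of the combined protocol and SAP names one longitudinal method: "a time dependent analysis will be performed using a logistic generalized estimating equations (GEE) model". The model terms are given as follows: "As fixed factors group (treatment versus placebo: dummy variable), time, time squared and the interaction between group and time will be taken into account". For adjustment, "age, gender and BMI will be included AS confounding parameters". The only other method is a fallback: "When the outcome does not warrant a GEE approach a Chi square analysis with expectation will be performed".

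Task 1 bases its laboratory measurements on "fecal samples which will be obtained from the study participants every week during their participation in the study". These cover short-chain fatty acids, microbiota composition and metabolites, and intestinal inflammatory markers. Symptoms are recorded less often, with a "Gastrointestinal Symptom rating scale (GSRS) in the beginning and in the end of the interventional period".

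The documents do not mention drop-out, missed samples, weighting, imputation, the working correlation, the analysis population or a sensitivity analysis. They also do not list which outcomes enter the GEE. The weekly faecal outcomes are the natural reading. They are the only measurements explicitly described as weekly, and a squared time term needs at least three time points, which questionnaires at the beginning and end cannot supply.

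**The concern.** A GEE with no stated weighting or imputation is, by default, fitted to whatever samples are observed. It then compares the arms, visit by visit, among the people still providing stool. If the chance of providing a sample depends on earlier results, and that dependence differs between RG-I and maltodextrin, the observed groups drift apart over the weeks without any treatment effect. That drift falls on the group-by-time term, which is where a fibre effect on the time course would appear.

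The mechanism is plausible here. A daily fibre is compared with maltodextrin, gastrointestinal symptoms are already of interest, and the outcomes are gut markers that may differ between those who stay and those who leave. A fibre effect could be created or masked by who remains in the study. Another choice of standard error would not help, because the problem lies in the estimate itself.

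**Working it through.** **Inputs from the documents.** The model terms and covariates are quoted above. The test is a "two-sided statistical evaluation at a significance level of 0.05", and "The groups will be of equal size". There is no sample size, power, event rate, drop-out rate or number of weeks, so there is no planned figure to reproduce and everything below is illustrative.

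**Condition for validity.** The GEE solves sum over participants of D'V⁻¹(Y − μ) = 0, using observed visits. At the true parameters this has mean zero if E(Y | observed, covariates) = μ. That holds when missingness is completely at random. It also holds when missingness depends only on covariates in a correctly specified μ. In general it fails when missingness depends on earlier or current outcomes.

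**Hand check of the mechanism.** Assume a binary outcome with baseline logit −0.4, so the proportion is 1/(1 + e^0.4) = 0.401. Let the active-arm hazard of leaving be 0.22 after a negative result and 0.03 after a positive one, and let the placebo hazard be 0.08 regardless. Ignoring covariates, the proportion of retained active participants whose last result was positive is

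0.401 × 0.97 / (0.401 × 0.97 + 0.599 × 0.78) = 0.455.

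On the logit scale the shift is ln(0.97/0.78) = 0.218. In placebo it is zero. If the same outcome-dependent hazards applied in both arms, both would shift alike and the difference would cancel when there is no true effect.

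**Logistic simulation.** This used 5 weekly visits, the planned terms with one standardised covariate standing in for age, gender and BMI, a latent AR(1) correlation of 0.85, and a true group-by-time log-OR of 0. Bias was measured at N = 200,000 (robust SE about 0.003). Type I error was measured with 1,000 replicates at total n = 100 (Monte Carlo SE √(0.05 × 0.95/1000) = 0.7 points).

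| Drop-out depends on | Retained at last visit, placebo/active | Log-OR per week, independence / exchangeable | Type I error, same order |
|---|---|---|---|
| nothing (0.90⁴ = 0.656) | 66% / 65% | 0.002 / 0.002 | 6.2% / 6.3% |
| arm and covariate | 74% / 53% | −0.002 / −0.001 | 5.8% / 5.0% |
| previous outcome, same in both arms | 63% / 63% | 0.001 / 0.002 | 5.4% / 5.1% |
| previous outcome, active arm only (placebo 0.92⁴ = 0.716) | 72% / 58% | 0.102 / −0.022 | 10.3% / 5.9% |
| current outcome, active arm only | 72% / 59% | 0.138 / 0.051 | 17.2% / 7.8% |

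Over four weeks, 0.102 per week becomes an odds ratio of exp(4 × 0.102) = 1.50 where the truth is 1.00. The exchangeable fit gives exp(4 × −0.022) = 0.92. With latent correlation 0.6 the last two rows became 0.051 / −0.013 and 0.101 / 0.072. With a true log-OR of 0.2 and correlation 0.85, the fourth row became 0.311 / 0.179. Weighting by the true inverse probabilities gave −0.007 to 0.006 when the truth was 0, and 0.197 to 0.204 when it was 0.2. That is an ideal result, because such weights cannot be estimated when drop-out depends on an unobserved outcome.

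**Linear simulation at lower drop-out.** This had 5 visits, within-person correlation 0.6 and no true effect. The per-visit hazard was k in placebo; in the active arm it was 2k after a high last value and 0 otherwise. Total drop-out is 1 − (1 − k)⁴.

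| k | Total drop-out | End-of-study bias, independence | Type I error, 30 per arm |
|---|---|---|---|
| 0.025 | 1 − 0.975⁴ = 10% | −0.05 SD | 5.9% |
| 0.05 | 1 − 0.95⁴ = 18% | −0.09 SD | 7.7% |
| 0.08 | 1 − 0.92⁴ = 28% | −0.16 SD | 10.8% |

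At 60 per arm with 18% drop-out, type I error was 10.9%. A random-intercept mixed model had bias of at most 0.01 SD and type I error of 5.7-5.9% at 30 per arm. An exchangeable GEE was nearly unbiased when it matched the true correlation, and a bias of about 0.01-0.03 SD remained under AR(1) truth. The sign is opposite to the logistic runs because here high values leave, whereas there negative results leave.

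**The case against.** Several points on the other side stand.

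- A reader might infer that the planned GEE is valid only if drop-out is completely at random. It is not so fragile. With 74% against 53% retention driven by arm and a model covariate, bias was −0.002 or smaller in size.
- A reader might infer that outcome-related drop-out would bias the result. It could, but drop-out depending on the previous outcome equally in both arms left group-by-time within 0.007 of the truth in every run.
- The larger biases from previous-outcome drop-out come from an independence working correlation, and the plan commits to none. With an exchangeable one the bias was small, and type I error (5.9%) was no worse than with completely random drop-out (6.3%).
- A reader might suppose that the plan relies on robust standard errors to make any working correlation safe. The documents mention neither robust errors nor working correlation, so no such position can be attributed to them.
- At 10% drop-out the type I error of 5.9% was no worse than that of the mixed model. The random-intercept model also matched the simulated correlation, so that comparison alone does not show that it beats a well-matched GEE.
- The simulated dependence is strong and confined to one arm, and this is a proof-of-concept study.

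It could also be said that this is only an unstated missing-data policy. That does not fully stand. An estimator is named, its default form needs a stronger assumption than readily available alternatives, and both the size and the direction of any bias turn on a choice left open.

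**Conclusion.** The point holds as a conditional risk. Under the default reading, the planned analysis assumes that missingness is unrelated to outcomes given group, time, age, gender and BMI. If drop-out or missed samples depend on earlier outcomes differently by arm, the group-by-time effect could be biased: materially under an independence working correlation, and only slightly under a well-matched one when the dependence is on observed values. If drop-out depends on the unobserved current outcome, some bias remained under either working correlation tried.

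This rests on two inferences from silence: that the GEE is unweighted and that it is applied to the weekly faecal outcomes. All magnitudes rest on assumed drop-out, visits, correlation and sample size. Symptom-related drop-out matters only if symptoms are related to the outcome given the covariates. The documents do not show that bias will occur. They show that the plan has not guarded against it. The change should be made, but the gap does not by itself invalidate the trial.

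**What to change.** Amend the Statistical Analysis section as follows.

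1. **Continuous weekly outcomes** (for example short-chain fatty acids and inflammatory markers): use a likelihood-based mixed model for repeated measures, including all randomised participants and all observed visits, with an unstructured or pre-specified best-fitting covariance and Kenward-Roger degrees of freedom. With mean and covariance adequately specified, this is valid when missingness depends on observed data.
2. **Truly binary outcomes:** keep the logistic GEE and name its working correlation. Fit it after multiple imputation by arm using earlier weekly outcome values and baseline GSRS, or with inverse-probability-of-observation weights. Imputation copes more easily with single missed samples.
3. Do not use an independence working correlation with unweighted incomplete data.
4. **Sensitivity analysis:** add one for drop-out that depends on unobserved outcomes, for example imputed values shifted by arm over a stated range. GSRS is taken only at the beginning and end, so no method here can condition on symptoms arising between those points.

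The cost is SAP wording, a covariance or imputation model to pre-specify, and slightly more analysis work with standard software. No new data are needed.

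### The start-and-end questionnaires have a start value that the planned analysis does not use as a covariate, which costs precision but not validity

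*Combined protocol and SAP*

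**What the plan says.** The STATISTICAL ANALYSIS section is a single paragraph. It specifies "a logistic generalized estimating equations (GEE) model via a stepwise approach". On covariates it says "age, gender and BMI will be included AS confounding parameters". The model terms are "group (treatment versus placebo: dummy variable" and "time, time squared and the interaction between group and time will be taken into account". The fallback is: "When the outcome does not warrant a GEE approach a Chi square analysis with expectation will be performed". Tests are two-sided at 0.05.

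Task 1 collects "a Gastrointestinal Symptom rating scale (GSRS) in the beginning and in the end of the interventional period"; the FFQ stands in the same sentence and, on the natural reading, shares that timing. Task 2 collects the IPAQ and EQ-5D-5L at the same two times. Stool outcomes follow another schedule: "fecal samples which will be obtained from the study participants every week during their participation in the study". The documents do not say whether the first stool sample comes before the first capsule.

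The STUDY PROTOCOL section names two RG-I sources: "The plant cell wall derived RG-I (from chicory or carrot) and maltodextrin (placebo) in capsuled form".

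**The concern.** A start value is usually the strongest predictor of the end value of the same questionnaire. The plan collects it but does not list it among the covariates. Two-time-point outcomes then have two possible routes, and the plan does not say which applies.

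- **GEE route.** The start value enters as the first response, and group-by-time is a between-group comparison of change. With two times, time squared adds nothing.
- **Chi-square route.** If the test is applied to the end value, the start value is not used at all.

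What is at stake is power in a proof-of-concept study. Neither route is biased under randomisation, but each discards information that the trial pays to collect.

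There is a secondary gap for the weekly stool outcomes. Group and group-by-time are both in the model, and neither is named as the test. With an interaction present, the group coefficient is the difference at time zero, while group-by-time is the difference in trend. These answer different questions, and their power depends on when an effect appears.

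**Working it through.** The documents give no sample size, power, correlation, effect size or number of weeks, so there is no figure of the plan's own to reproduce. From the documents come equal groups, two-sided 0.05, the listed model terms and the questionnaire times. The rest is assumed: start-end correlation ρ of 0.3, 0.5 or 0.7, equal SD at both times and, for power, 60 per group with a 0.5 SD difference.

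**1. Redundant term.** With two times coded 0 and 1, time squared equals time. Under any other coding of two times it is a linear function of time and the intercept. The five columns (intercept, time, time squared, group, group-by-time) therefore have rank 4. In a worked two-visit fit, the group-by-time estimate, SE and p-value were the same with and without time squared (0.141, 0.441, 0.749). The term is redundant and harmless.

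**2. Variance for a score.** Per participant, in units of SD²:
- end value alone: 1
- change: 2(1 − ρ)
- end value adjusted for start: 1 − ρ²

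Adjusted against change: (1 − ρ²) / [2(1 − ρ)] = (1 + ρ)/2. Adjusted against end-only: 1 − ρ².

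| ρ | (1 + ρ)/2 | 1 − ρ² |
|---|---|---|
| 0.3 | 0.65 | 0.91 |
| 0.5 | 0.75 | 0.75 |
| 0.7 | 0.85 | 0.51 |

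The adjusted analysis has the smallest variance in every row.

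**3. Power for a score.** Power = Φ(0.5 / √(V × 2/60) − 1.96), where V is the variance from step 2. For end-only, 0.5/√(2/60) = 2.74, so power is Φ(0.78) = 78%.

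| ρ | Adjusted | Change | End-only |
|---|---|---|---|
| 0.3 | 82% | 64% | 78% |
| 0.5 | 89% | 78% | 78% |
| 0.7 | 97% | 94% | 78% |

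Simulation with 10,000 trials per setting gives 80/87/96%, 62/76/94% and 77/77/76%, within about 2 points.

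**4. Binary start-and-end outcome.** This was simulated with 60 per group, prevalence 50% and latent correlation 0.3/0.5/0.7. Group-by-time in the logistic GEE has 80/80/79% power. Logistic regression of the end value on group and start value has 94/92/88%. The latent effect was set separately at each correlation (0.845/0.77/0.67 SD) to hold the GEE near 80%, so only the gap within each correlation is meaningful.

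**5. Weekly stool outcome.** This was simulated as a binary marker with 60 per group, 5 samples, correlation 0.5, prevalence 40% and a latent shift of 0.6 SD. If every sample is on treatment and the effect is constant, the true difference in trend is zero, so group-by-time rejects at about its null rate of 5%. The final-week difference has 87% power and the average difference 97%.

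If a pre-intervention sample exists and is used as a covariate, with the four later samples as outcomes:
- immediate, sustained effect: final-week 89%, average 99%
- effect that builds up: final-week 88%, average 74%

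Neither contrast wins in every case.

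**The case against.** The strongest reply is that the planned GEE does not ignore the start value. If it is the first response and group-by-time is the test, the result is a legitimate comparison of change. That stands: covariate adjustment improves precision and does not correct an error. The gap to change-score analysis also narrows as the correlation rises (variance ratio 0.85 at 0.7).

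It is also fair that this is a proof-of-concept study and that every power figure rests on assumed inputs. The ordering of the variances does not, because (1 + ρ)/2 and 1 − ρ² are below 1 for any positive correlation below 1.

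A reader might infer three stronger things that the documents do not support.

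- **That stepwise means removing terms on their p-values.** The plan says the covariates will be included and the fixed terms taken into account. This reads as forced entry, so stepwise may mean only a crude model followed by an adjusted one. The word needs defining; it does not establish data-driven selection.
- **That the false-positive rate is 8–10% rather than 5%.** That needs a rule under which either group or group-by-time may count as the effect. With five visits coded 0 to 4, such a rule gives 8.7/9.1/9.4% at correlation 0.3/0.5/0.7, and 1 − 0.95² = 9.75% if the two tests were independent. The plan does not state the rule, although it does not exclude it.
- **That the final-week difference is the right test for stool outcomes.** Step 5 shows a trade-off. In addition, if a pre-intervention sample is kept as an outcome, a linear group-by-time term misfits an immediate effect. A line fitted to true differences 0, 1, 1, 1, 1 at times 0 to 4 has intercept 0.4 and slope 0.2, so it gives 0.4 + 4 × 0.2 = 1.2 at the final week, where the truth is 1.0.

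**Conclusion.** The point holds as a loss of precision for the start-and-end questionnaires. The plan lists no start value as a covariate although it collects one, and either route it leaves open is valid but less efficient. At correlations of 0.3 to 0.7, adjustment leaves 65–85% of the change-score variance and 91–51% of the end-only variance. With 60 per group and a 0.5 SD difference, the gain is 3 to 18 points of power over change and 4 to 19 points over end-only (step 3, normal approximation). Those sizes depend on the assumed correlation, sample size and effect, none of which the documents give. The score figures also assume a linear analysis; the plan does not say how a score would enter a logistic model or a chi-square, and no loss from cutting scores into categories is counted here.

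Omitting the covariate causes no bias, and no inflated error rate is shown. The unnamed test for the stool outcomes, the undefined stepwise procedure and the pooling of the two RG-I sources are missing details to be settled before unblinding. The change is worth making, with medium confidence.

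**What to change.** **Main change, start-and-end questionnaires.** Regress the end value on group, start value, age, gender and BMI. Use an identity link with robust SE for scores and a logit link for binary outcomes. Include no time terms, remove no term on its p-value, and test the group coefficient at two-sided 0.05. This replaces both the GEE with time terms and the chi-square for these outcomes.

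**Secondary clarifications.**
- Weekly stool outcomes: name one group contrast in advance as the test. The choice between final-week and average difference is the sponsor's and depends on when an effect is expected. If a pre-intervention sample exists, use its value as a covariate and only the later samples as outcomes.
- Stepwise: say what it means. If it is crude then adjusted, name the fully adjusted model as the result.
- RG-I sources: state whether chicory and carrot are pooled, which fits the single dummy, or each compared with placebo. Separate comparisons need two dummies and a multiplicity rule; two unadjusted 0.05 tests sharing a placebo group (correlation 0.5) give a 9.1% chance of at least one false positive.

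**Cost.** No new questionnaire data are needed. The start value uses one degree of freedom per model, and the plan needs a rule for missing start values. For binary outcomes the odds ratio becomes conditional on the start value. For scores the logistic model gives way to a linear one, which is a change of model and should be stated as such. Error remains controlled per outcome, not across the many outcomes in Tasks 1 and 2.
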